2. STUDY OBJECTIVES AND ENDPOINTS

| OBJECTIVES | ENDPOINTS |
|---|--|
| Primary | Primary |
| 
 To assess the safety and tolerability of TMP-301 following multiple ascending oral doses | 
The primary endpoint is safety assessed after multiple-dose administrations by:
 
 Adverse events (AE) Clinical laboratory tests Vital sign measurements 12-lead electrocardiograms (ECG) Physical examinations Psychiatric assessments (Brief Psychiatric Rating Scale [BPRS], Clinician-Administered Dissociative States Scale [CADSS], Columbia Suicide Severity Rating Scale [C-SSRS], Modified Mini-Mental State Examination (3MS) and Visual Analogue Scale [VAS]) |
| Secondary | Secondary |
| 
 To assess the pharmacokinetics (PK) profile of TMP301 following multiple- ascending- oral doses | 
The secondary objective will be assessed with the following endpoints:
 
 Day 1: Partial areas defined as AUC_{0-12} and AUC_{0-24}; maximum concentration (C_{max}), time of maximum concentration (T_{max}), concentration at 12 h (C_{12}), concentration at 24 h (C_{24}) where $C_{24} = C_{trough Day2}$ Day 14 (or last day of dosing): AUC_{ss} from time zero to the time the end of the (12 or 24 hour) dosing interval ($AUC_{0-TAU,ss}$). For BID cohorts, $AUC_{0-TAU,ss} = AUC_{0-12,ss}$, and for QD cohorts, $AUC_{0-TAU,ss} = AUC_{0-24,ss}$; $C_{avg,ss}$, $C_{max,ss}$, $T_{max,ss}$, $C_{12,ss}$, $C_{24,ss}$, and $C_{min,ss}$, all at steady-state (SS), along with apparent total plasma clearance (CL/F) and apparent volume of distribution (V_z/F) • |
| Exploratory | Additional PK evaluations |

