| 
 To assess endpoints related to TMP-301 mechanism of action To evaluate CYP1A2 genotypes and their association with phenotypes for potential impact on metabolism and to identify biomarkers of potential response to TMP-301. Identify TMP-301 metabolites in urine | 
 Accumulation ratio derived as: 
 $AR_{AUC_{0-12}} BID = AUC_{0-12,ss} / AUC_{0-12, Day 1}$ $AR_{AUC_{0-24}} QD = AUC_{0-24,ss} / AUC_{0-24, Day 1}$ $AR_{C_{max}} = C_{max,ss} / C_{max,FD, Day 1}$ $AR_{C_{12}} = C_{12,ss} / C_{12, Day 1}$ $AR_{C_{24}} = C_{24,ss} / C_{24, Day 1}$ Estimations of dose proportionality at steady state. Dose-normalized PK parameters (C_{max}, C_{12}, C_{24}, and AUC_{0-12} and AUC_{0-24}, when appropriate) will be |

| OBJECTIVES | ENDPOINTS |
|------------|---|
| | 
assessed graphically for dose-proportionality
 
 • Estimation of time to achieve steady state. (C_{trough} will be displayed graphically and summarized descriptively by day to assess for steady state) • As a marker of CYP1A2 activity, the ratio of paraxanthine to caffeine concentration (at 4 hours post caffeine dose) will be reported on Day -1 and Day 14. Change in CYP1A2 activity will be derived as $CYP1A2_ratio = \frac{\text{paraxanthine/caffeine concentration day 14}}{\text{paraxanthine/caffeine concentration day -1}}$ |

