3.3. Overall Study Design

This study will be a randomized, double-blind, placebo controlled, fixed sequence, MAD study. The study will be conducted in a single clinical research unit (CRU). The study will consist of up to 4 cohorts. Each cohort will consist of 8 subjects (6:2 for active: placebo), for a maximum total sample size of approximately 32 subjects. Subjects will only participate in 1 cohort.

Screening will occur within approximately 28 days prior to the first scheduled study drug administration. Screening data will be reviewed to determine subject eligibility. Subjects who meet all inclusion criteria and none of the exclusion criteria and who consent to participation will be admitted to the CRU for baseline evaluations prior to dosing. All baseline safety results should be available prior to the first study drug administration.

In cohort 2, subjects will be fasted overnight for 10 hours prior to the morning dose, followed by a 2 hour fast. Subjects were fasted for 2 hours prior to dosing and 2 hours following the evening dose for the cohort 1 (50 mg bid). If dosing in a fed condition is selected for cohort 3 or 4 (see section 3.1), subjects will be fasted overnight for approximately 9 hours, then given standard breakfast followed by study treatment dosing 30 minutes after initiation of breakfast.

Each subject will be randomly assigned to 1 of the following cohorts:

- Cohort 1: Group 1 (6 subjects): 50 mg of TMP-301 bid
Group 2 (2 subjects): placebo (matching TMP-301) bid
- Cohort 2: Group 3 (6 subjects): 50 mg of TMP-301 qd
Group 4 (2 subjects): placebo (matching TMP-301) qd
- Cohort 3: Group 5 (6 subjects): Dose regimen of TMP-301 to be determined
Group 6 (2 subjects): placebo (matching TMP-301)
- Cohort 4: Group 7 (6 subjects): Dose regimen of TMP-301 to be determined
Group 8 (2 subjects): placebo (matching TMP-301)

Safety will be assessed and blood samples for PK will be collected throughout confinement. Subjects will be discharged from the CRU on Day 18. Subjects will return to the CRU on Day 25 for a follow-up visit and EOS procedures.

Caffeine (100 mg) will be included as probe CYP1A2 substrate in cohort 2 and subsequent cohorts. Ratio of plasma paraxanthine/caffeine will be determined in a blood sample 4 hours after administration of caffeine at baseline (Day-1) and on day 14.

The maximum duration of subject participation, including Screening, will be approximately 53 days.

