5.3. Administration of Study Drug

For cohort 1, the study drug will be administered twice daily (12 hours apart) on Days 1-13 and once in the morning on Day 14. For cohort 2 (and Cohorts 3-4 if done) the study drug will be administered once daily in the morning on Days 1-14. The date and time of each dose will be recorded. For each subject, all scheduled post dose activities and assessments will be performed relative to the time of the first study drug administration.

Commercially Confidential Information

On Day -1, caffeine will be administered at approximately 9:00 am with approximately 240 mL of water at ambient temperature test. On Day 14, caffeine will be administered with the study drug and approximately 240 mL of water.

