^c Clinical Interview for DSM-5 (SCID-5 CT) will be conducted by appropriately trained staff. This psychiatric examination will include an assessment of premorbid personality, personal and developmental history, alcohol and substance use history, forensic history, past psychiatric history. The PRIME questionnaire will also be administered to screen for risk of psychosis. A psychiatric exam (full or partial) can take place at any time during the study at the discretion of the PI, if there is a relevant concern.

^d In all females. Serum pregnancy test at Screening and urine pregnancy tests at all other times. A positive urine pregnancy test will be confirmed with a serum pregnancy test.

^e In all females to determine postmenopausal status.

^f Height measured at Screening only.

^g The genotyping samples will be stored and may be processed and analyzed to assess genotyping of drug metabolizing systems.

^h Day 1 at pre-dose, 1, 4, and 8 hours; day 2 pre-dose; and days 7 and 14 at pre-dose, 1, 4, and 8 hours.

ⁱ For BID Cohorts: Dosing twice daily interval from Day 1 to Day 13, two intakes separated by 12.00 hours (note: only the AM dose is administered on Day 14). For QD Cohorts: Dosing once daily in the morning from Day 1 to Day 14.

^j Timing of PK blood samples may be changed based on emerging data.

^k At each protocol specified timepoint for PK (including predose baseline) out to 12.00 hours postdose. (Section 6.2).

¹ Serial blood will be collected on Day 1, and 14 at predose, 0.5, 1.00, 2.00, 3.00, 4.00, 6.00, 8.00, and 12.00 hours. Trough (predose AM) and 8 hr and 12 hr samples will be collected on Days 2, 7 and 11. Trough samples (predose AM) will be collected on Days 5, 9 and 12. Additional PK samples will be drawn after the last dose on Day 14 at 24.00 (Day 15), 28.00 (Day 15), 48.00 (Day 16), 52.00 (Day 16), 72.00 (Day 17), and 96.00 (Day 18) hours postdose and Day 25 at the follow-up EOS visit (Day25 ± 2 days). Urine will be collected on Day 1 (0 to 4, 4 to 8, 8 to 12, 12 – 24 hr) and Day 14 (0 to 4, 4 to 8, 8 to 12, 12 to 24, 24 to 48 (Day 15), and 48 – 72 hr (Day 16)). See [Table 4](#).

^m Day 1 predose, then 24.00 (Day 2) and 72.00 hours (Day 4) postdose, then every 2 days (Days 6, 8, 10, 12, 14, 16) post dose at approximately 10 am ± 1 hour.

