10.4 Non-Compartmental Analysis

The following configuration for the NCA analysis (with Phoenix® WinNonlin® version 8.0, or higher) will be used:

• Data:	Serial sampled data
• Model/Dose options Type:	Plasma (200 -202) / Extravascular
• AUC Calculation Method:	Linear Up Log Down
• Lambda z (λ_z) calculation:	Best fit method for λ_z Linear-Log regression

Reasons for excluding PK parameters will include the following:

- AUC: AUC parameters will not be estimated if less than 3 consecutive measurable concentrations are observed
- PK parameters requiring λ_z estimation (eg, Vz/F) will be set to Not Reported (NR) in the tables and listings if they meet one of the following:
 - $R^2 < 0.8$

The PK parameters for TMP-301 are presented in Table 6.

Table 7: Pharmacokinetic Parameters of TMP-301

Parameter	Definition
PK Parameters Day 1	
C_{\max}	Maximum observed concentration occurring at time T_{\max} after the first dose
T_{\max}	Time of maximum observed concentration after the first dose
AUC_{0-12} , (For BID dosing)	Area under the concentration time curve over the dosing interval, calculated from 0 to 12 hours (dosing interval) after the first dose (The nominal time will be used to estimate AUC using the NCA built-in tool in Phoenix® WinNonlin®. This means that actual times off by more than 1 minute from tau will be extrapolated/intrapolated as per Phoenix® WinNonlin®'s built-in formulas. If extrapolation/intrapolation is not possible, then no value is reported by the software.)
AUC_{0-24} , (For QD dosing)	Area under the concentration time curve over the dosing interval, calculated from 0 to 24 hours (dosing interval) after the first dose (The nominal time will be used to estimate AUC using the NCA built-in tool in Phoenix® WinNonlin®. This means that actual times off by more than 1 minute from tau will be extrapolated/intrapolated as per Phoenix® WinNonlin®'s built-in formulas. If extrapolation/intrapolation is not possible, then no value is reported by the software.)
C_{12}	Observed concentration occurring at time 12 h
C_{24}	Observed concentration occurring at time 24 h (C_{24} Day 1 = C_{trough} Day 2)
PK Parameters Days 2, 5, 7, 9, 11 and 12	
C_{trough}	Observed concentration at the end of the dosing interval
PK Parameters Day 14	
$C_{\max, ss}$	Maximum observed concentration at steady -state occurring at time $T_{\max, ss}$
C_{avg}	Average concentration, calculated as $AUC_{0-\text{Tau}, ss}/\text{Tau}$

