$T_{\max, ss}$	Time of maximum observed concentration at steady-state
$C_{\min, ss}$	Minimum observed concentration after the first dose of a multiple regimen
$AUC_{0-\text{TAU}, ss}$	Area under the concentration time curve over the dosing interval at steady-state. (The nominal time will be used to estimate AUC using the NCA built-in tool in Phoenix® WinNonlin®. This means that actual times off by more than 1 minute from tau will be extrapolated/intrapolated as per Phoenix® WinNonlin®'s built-in formulas. If extrapolation/intrapolation is not possible, then no value is reported by the software.) For QD dosing: $AUC_{0-\text{TAU}, ss} = AUC_{0-24, ss}$ For BID dosing $AUC_{0-\text{TAU}, ss} = AUC_{0-12, ss}$
$C_{12, ss}$	Observed concentration occurring at time 12 h

Parameter	Definition
$C_{24,ss}$	Observed concentration occurring at time 24 h
CL/F	Apparent total clearance at steady-state, calculated as Dose/ $AUC_{0-TAU,ss}$
V_z/F	Apparent volume of distribution at steady-state, calculated as Dose/ λ_z * $AUC_{0-TAU,ss}$
AR_C _{max}	Accumulation ratio derived as $C_{max,ss} / C_{max,FD\ Day\ 1}$
AR_AUC _{0-12 BID}	Accumulation ratio derived as $AUC_{0-12,ss} / AUC_{0-12,Day\ 1}$
AR_AUC _{0-24 QD}	Accumulation ratio derived as $AUC_{0-24,ss} / AUC_{0-24,Day\ 1}$
AR_C ₁₂	Accumulation ratio derived as $C_{12,ss}/C_{12,Day\ 1}$
AR_C ₂₄	Accumulation ratio derived as $C_{24,ss}/C_{24,Day\ 1}$ ($C_{24\ Day\ 1} = C_{trough\ Day\ 2}$)
CYP1A2_ratio	Ratio of CYP1A2 activity derived as paraxanthine/caffeine concentration day 14 / paraxanthine/caffeine concentration day -1
The following PK parameters will be used for PK calculation on Day 14 and presented in the PK listings only	
λ_z Upper	Upper limit on time for values included in the calculation of λ_z
λ_z Lower	Lower limit on time for values included in the calculation of λ_z
λ_z	Apparent elimination rate constant, estimated by linear regression of the terminal linear portion of the log concentration versus time curve
R ²	Goodness of fit for the terminal phase
Number of Points	Number of data points in computing λ_z

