10.6.2 Dose Proportionality

Natural log-transformed PK parameters ($C_{\text{max, ss}}$, $C_{12, \text{ss}}$, $C_{24, \text{ss}}$, and $AUC_{0-\text{TAU, ss}}$) will be assessed statistically for proportionality. Proportionality analysis will be done using a power model. The power model is defined as:

$$\ln(\text{PK parameter}) = \alpha + \beta \cdot \ln(\text{Dose}) + \varepsilon$$

where α is the intercept, β is the slope and ε is the error term. A linear model with ln-transformed dose as a continuous effect will be fitted. A point estimate and a 90% confidence interval will be derived for the slope (β).

The parameter can be considered to be dose-proportional if the 90% CIs for the slope coefficient that include 1 will suggest evidence of dose proportionality.

Dose proportionality may be assessed within different dose ranges if deemed appropriate with at least three doses.

Otherwise, if there are only two cohorts completed, Statistical inference will be based on a bioequivalence approach for a parallel group design and expressing the relative difference as a geometric mean ratio and 90% CI using ANOVA model based on dose normalized PK parameters.

No comparison between fed and fast state will be provided.

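### In BID cohorts C24,ss is a value 24 h after the last dose, not a steady-state trough, and AR_C24 built on it understates accumulation; restrict both to QD

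*SAP*

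**What the plan says.** SAP Table 7 lists C24,ss for Day 14 as "Observed concentration occurring at time 24 h". The accumulation ratio is defined in Protocol section 2 as "AR_{C_{24}} = C_{24,ss} / C_{24, Day 1", and SAP Tables 1 and 7 repeat it. Day 1 C24 is set equal to the Day 2 trough. Protocol section 2 places C24,ss among the Day 14 values that are "all at steady-state (SS".

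Table 7 ties AUC to the regimen: the Day 1 AUC0-12 row is marked "For BID dosing", AUC0-24 is marked for QD, and the two AUC accumulation ratios are split the same way. The C24,ss and AR_C24 rows carry no such mark.

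For BID cohorts, footnote i of Protocol Table 3 adds: "note: only the AM dose is administered on Day 14". Protocol Table 4 counts nominal times from that day's morning dose.

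Cohort 1 (50 mg BID, 6 active and 2 placebo) is the only certain BID cohort. Protocol 5.3 says: "For cohort 2 (and Cohorts 3-4 if done) the study drug will be administered once daily in the morning on Days 1-14". Protocol 3.3, however, still describes cohorts 3 and 4 as "Dose regimen of TMP-301 to be determined".

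**The concern.** An accumulation ratio should compare the same time since the last dose, once after the first dose and once at steady state. For QD dosing AR_C24 does this: both samples are 24 h after a dose. For BID dosing it does not. The Day 1 sample is 12 h after the evening dose and the Day 14 sample is 24 h after the last dose.

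Two outputs are affected. A named secondary endpoint, C24,ss, would be reported for cohort 1 as a steady-state value although an evening dose has been left out. An additional PK evaluation, AR_C24, would read too low. A reader could take it as evidence of little or no accumulation beside an AR_C12 that shows a clear rise.

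**Working it through.** **Inputs.** BID dosing is 27 doses 12 h apart (Protocol Table 2). With the first dose at 0 h, the last is at 26 × 12 = 312 h, the morning of Day 14. The BID samples then fall as follows:

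| Parameter | Clock time | Time since last dose |
|---|---|---|
| C12, Day 1 | 12 h (before the evening dose) | 12 h |
| C24, Day 1 (Day 2 trough) | 24 h | 12 h |
| C12,ss | 324 h | 12 h |
| C24,ss | 336 h | 24 h |

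The two C12 samples match. The two C24 samples do not. The documents give no accumulation ratio and the half-life is redacted, so there is no figure in the plan to reproduce.

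**Step 1: direction, with no compartment model.** Let f(t) be the concentration t hours after a single dose. Assume linear, time-invariant PK with equal morning and evening exposure. By superposition:

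- AR_C12 = [f(12) + f(24) + f(36) + …] / f(12)
- AR_C24 = [f(24) + f(36) + …] / [f(12) + f(24)]

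The second ratio has a smaller numerator and a larger denominator, so AR_C24 is below AR_C12.

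**Step 2: size, if the drug is also one-compartment.** Let r = 2^(−12/t½). After absorption, with A a constant:

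- C12, Day 1 = A·r
- C24, Day 1 = A·r·(1 + r)
- C12,ss = A·r/(1 − r)
- C24,ss = A·r²/(1 − r)

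Hence AR_C12 = 1/(1 − r), AR_C24 = r/(1 − r²), their ratio is r/(1 + r), and C24,ss/C12,ss = r. Since r is below 1, r/(1 + r) is below 0.5.

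At an assumed half-life of 12 h, r = 0.5. Then AR_C12 = 1/0.5 = 2.00, AR_C24 = 0.5/0.75 = 0.67, and the ratio is 0.5/1.5 = 0.33. Summing over the 27 actual doses for a range of assumed half-lives gives:

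| Assumed t½ (h) | r | AR_C12 | AR_C24 | AR_C24/AR_C12 | C24,ss/C12,ss |
|---|---|---|---|---|---|
| 8 | 0.354 | 1.55 | 0.40 | 0.26 | 0.35 |
| 12 | 0.500 | 2.00 | 0.67 | 0.33 | 0.50 |
| 18 | 0.630 | 2.70 | 1.04 | 0.39 | 0.63 |
| 24 | 0.707 | 3.41 | 1.41 | 0.41 | 0.71 |
| 36 | 0.794 | 4.84 | 2.14 | 0.44 | 0.79 |

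With first-order absorption added, over half-lives of 2–200 h and absorption half-lives of 0.1–60 h, the largest AR_C24/AR_C12 is 0.49.

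**Step 3: when AR_C24 reads below 1.** Setting r/(1 − r²) = 1 gives r = 0.618, so t½ = 12·ln 2/(−ln 0.618) = 17.3 h. At that half-life AR_C12 is 1/(1 − 0.618) = 2.62.

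**Step 4: how far the one-half bound depends on its assumptions.** It is not universal. In the cases tried, AR_C24/AR_C12 reached:

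- about 0.58 with a marked two-phase decline (half-lives 4 h and 120 h, slow phase 5% of the intercept);
- 0.53 if the half-life lengthens from 12 h to 36 h by Day 14;
- 0.51 if evening exposure is 0.8 of morning exposure at a 48 h half-life, from r/(p + r) with p = 0.8 and r = 0.841.

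The ratio stayed below 1 in all of these.

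**Step 5: QD check.** For QD dosing AR_C24 = 1/(1 − r²), which is 1.33 at 12 h and 2.00 at 24 h. This is the correct QD accumulation, so QD cohorts are not affected.

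**The case against.** The strongest reply is that little turns on this. The Table 7 wording for C24,ss is literally accurate, and a pharmacokineticist can see the last-dose timing in Protocol Table 4. Accumulation ratios are additional evaluations. For BID, C12,ss, AR_C12, AR_Cmax and AR_AUC0-12 are planned and valid, and the escalation limits in Protocol Table 1 are set on AUC0-24 and Cmax. All of this stands, and it makes the point minor. It does not make the rows right: Table 7 followed as written produces the mislabelled value and the low ratio, and SAP section 12 records no exception. The qualifier *when appropriate* in SAP 10.6.1 covers only the dose-normalised graphs.

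A second objection concerns size. A reader might infer that AR_C24 is less than half of AR_C12 whatever the drug's kinetics. The documents do not support that. The kinetics are redacted, the fast before dosing is 10 h in the morning and 2 h in the evening (Protocol 5.4), and the study itself examines whether CYP1A2 activity changes by Day 14. The bound holds only under the conditions in Step 2.

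A third tempting inference is that the BID C24,ss is what distorts the dose-proportionality analysis, most visibly in the two-cohort fallback, where "Statistical inference will be based on a bioequivalence approach for a parallel group design". For a linear one-compartment drug, the per-dose C24,ss ratio of BID to QD is [r²/(1 − r)]/[r²/(1 − r²)] = 1 + r, not 1. But C12,ss gives the same factor: [r/(1 − r)]/[r/(1 − r²)] = 1 + r. It comes from mixing regimens, not from the washout timing, and the change proposed here does not cure it. It is no evidence for this point.

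**Conclusion.** The point holds as a minor correction for cohort 1 and any later BID cohort. That C24,ss is not a steady-state trough under BID dosing, and that AR_C24 compares different times since the last dose, follows from the dosing and sampling schedule alone. That AR_C24 is below AR_C12 needs linear, time-invariant PK with equal morning and evening exposure. The factor r/(1 + r), always below 0.5, also needs one-compartment kinetics. The tabulated values rest further on assumed half-lives, and AR_C24 reads below 1 only if the half-life is under about 17.3 h. Neither QD results nor escalation decisions are affected.

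**What to change.** - In SAP Table 7, and in the matching SAP Table 1 entries, restrict C24,ss and AR_C24 to QD cohorts, as the AUC rows already are.
- For BID cohorts, report the planned C12,ss as the steady-state trough, and AR_C12, AR_Cmax and AR_AUC0-12 for accumulation. No new ratio is needed.
- Label the BID Day 15 sample as 24 h after last dose. Keep it for estimating λz, but do not carry it as C24,ss into SAP 10.6.1 or 10.6.2.
- Record the change in SAP section 12, because the protocol lists both parameters without a regimen limit.

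The cost is two Table 7 rows, the matching Table 1 entries, a sentence each in 10.6.1 and 10.6.2, and one section 12 entry. Dosing and sampling do not change. One output is lost: if only cohorts 1 and 2 are completed, C24,ss has no dose-proportionality comparison. How BID and QD cohorts should be combined in 10.6.2 remains a separate question.

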3 STUDY DESIGN

3.1 General Description

This study will be a randomized, double-blind, placebo -controlled, fixed -sequence, MAD study. The study will be conducted in a single clinical research unit (CRU). The study will consist of up to 4 cohorts. Each cohort will consist of 8 subjects (6:2 for active: placebo), for a maximum total sample size of approximately 32 subjects. Subjects will only participate in 1 cohort.

Screening will occur within approximately 28 days prior to the first scheduled study drug administration. Screening data will be reviewed to determine subject eligibility. Subjects who meet all inclusion criteria and none of the exclusion criteria and who consent to participation will be admitted to the CRU for baseline evaluations prior to dosing. All baseline safety results should be available prior to the first study drug administration.

In cohort 2, subjects will be fasted overnight for 10 hours prior to the morning dose, followed by a 2 hour fast. Subjects were fasted for 2 hours prior to dosing and 2 hours following the evening dose for the cohort 1 (50 mg bid). If dosing in a fed condition is selected for cohort 3 or 4, subjects will be fasted overnight for approximately 9 hours, then given breakfast followed by study treatment dosing 30 minutes after initiation of breakfast.

Each subject will be randomly assigned to 1 of the following cohorts:

- Cohort 1:
 - Group 1 (6 subjects): 50 mg of TMP-301 bid
 - Group 2 (2 subjects): placebo (matching TMP-301) bid

- Cohort 2:
 - Group 3 (6 subjects): 50 mg of TMP-301 qd
 - Group 4 (2 subjects): placebo (matching TMP-301) qd

- Cohort 3:
 - Group 5 (6 subjects): Dose regimen of TMP-301 to be determined
 - Group 6 (2 subjects): placebo (matching TMP-301)

- Cohort 4:
 - Group 7 (6 subjects): Dose regimen of TMP-301 to be determined
 - Group 8 (2 subjects): placebo (matching TMP-301)

Safety will be assessed and blood samples for PK will be collected throughout confinement. Subjects will be discharged from the CRU on Day 18. Subjects will return to the CRU on Day 25 for a follow-up visit and End-of-Study (EOS) procedures.

Caffeine (100 mg) will be included as probe CYP1A2 substrate in cohort 2 and subsequent cohorts. Ratio of plasma paraxanthine/caffeine will be determined in a blood sample 4 hours after administration of caffeine at baseline (Day-1) and on day 14.

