4 ANALYSIS POPULATIONS

- **Enrolled Population**

The Enrolled population will include all subjects who signed the informed consent form (ICF).

- **Screened Population**

The Screened population will include all subjects who meet the eligibility criteria.

- **Randomized Population**

The Randomized population will include all subjects who are assigned a randomization number.

- **Safety Population**

The Safety population will include all subjects who received at least 1 dose of one of the investigational product (IP) or placebo. The number of subjects who were included, who discontinued, and who completed the study will be tabulated. The primary reasons for discontinuation will be provided.

- **Pharmacokinetic (PK) Population**

The PK population will include all subjects who have received at least 1 dose of the investigational product and have sufficient PK data to derive at least 1 PK parameter.

Subjects who do not complete the sampling schedule may be included in the PK analysis for only the PK parameters that are judged not to be affected by the missing sample(s).

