5.2 Pharmacokinetic Analysis

In general, all PK summary tables will be presented for the PK population.

Individual raw PK concentrations will be displayed with the same precision as received from the bioanalytical laboratory.

Precision for individual PK parameters will be displayed as follows:

- C_{\max} , C_{\min} , CL/F , Vz/F and AUCs will be displayed with the same precision as the raw PK concentration data
- Parameters associated with time (eg, time of maximum concentration [T_{\max}]) will be displayed with 2 decimal places
- Percentages will be displayed with 2 decimal places
- Ratios will be displayed with 2 decimal places
- Coefficient of determination (R^2) and elimination rate constant (λ_z) will be displayed with 4 decimal places

Summary statistics for concentration and PK parameters will be displayed with the same precision as the individual values, with the exception of number of observations (n) and CV% which will be presented with 0 and 1 decimal place, respectively.

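### The caffeine-probe CYP1A2 ratio is planned only as a descriptive before/after summary, with no comparison against placebo and no clear statement that placebo subjects are included

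*SAP*

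**What the plan says.** SAP section 10.4 defines the parameter as "Ratio of CYP1A2 activity derived as paraxanthine/caffeine concentration day 14 / paraxanthine/caffeine concentration day -1". It stands in the table headed "Table 7: Pharmacokinetic Parameters of TMP-301". SAP section 2 and Protocol section 2 place it under the exploratory objectives and call it the change in CYP1A2 activity.

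The analysis is descriptive. SAP section 10.6.1 gives summary statistics for all PK parameters, and section 10.6 stratifies PK outputs by treatment where appropriate. No contrast is specified for this ratio. The SAP does plan modelled contrasts with pooled placebo for BPRS, CADSS and 3MS (section 9.6).

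On who is analysed, SAP section 5.2 says: "In general, all PK summary tables will be presented for the PK population". SAP section 4 defines that population as "all subjects who have received at least 1 dose of the investigational product and have sufficient PK data to derive at least 1 PK parameter". The Safety population in the same section is "all subjects who received at least 1 dose of one of the investigational product (IP) or placebo".

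On who takes the probe, SAP section 3.1 says: "Caffeine (100 mg) will be included as probe CYP1A2 substrate in cohort 2 and subsequent cohorts". Each cohort is 6 active to 2 placebo, and caffeine is not limited to the active arm.

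**The concern.** The probe is given before dosing and again after 14 days of study drug, so a reader will take a change in the ratio as evidence on whether TMP-301 alters CYP1A2 activity. Day -1 and Day 14 differ in more than exposure to TMP-301, and a before/after summary in active subjects carries all of those differences. A randomised control that could remove the shared part is built into the design, but no planned comparison uses it.

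The population wording adds a second gap. If placebo subjects are left out, the reader has no reference at all. If they are kept in, the reader sees two descriptive columns and no estimate of the difference. The SAP does not say which applies.

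**Working it through.** **No figure to reproduce.** Neither document gives an expected effect, a variability or a sample-size basis for this ratio. SAP section 3.5 states that no formal calculation was done.

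**Is placebo in the PK population?**
- Pointing to exclusion: SAP section 4 names placebo for Safety but not for PK, and SAP section 3.2 lists IP and placebo as separate items.
- Pointing to inclusion: Protocol section 5.1 counts placebo among the IPs. Protocol section 8.1.2 accepts an equivalent of the study drug and a concentration in any matrix. A placebo subject with both caffeine samples has one derivable parameter from the SAP's own table.
- Result: undefined.

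**What differs between the two probe days?**
- *Site diet.* Admission is on Day -2 in the evening (Protocol synopsis) and the Day -1 probe is at about 9:00 am (Protocol 5.3), so the baseline follows less than one day of site food. Day 14 follows about two weeks.
- *Caffeine abstinence.* It starts 48 h before check-in (Protocol 4.4), so it has lasted about 2.5 days at the first probe. By Day 14 the only permitted caffeine in about two weeks was that probe.
- *Administration.* Caffeine is given with water on Day -1 and together with the study capsule on Day 14 (Protocol 5.3). Cohorts 3 and 4 may be dosed fed (Protocol 5.4). The visible text does not give the feeding state for the Day -1 probe.

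**Effect of a common shift.** Let *g* be the Day -1 to Day 14 shift shared by both arms and *d* the drug effect. The active-group ratio estimates *g × d*; active divided by placebo estimates *(g × d)/g = d*. The documents do not give *g*, so 0.80 to 1.25 is an assumed range.
- *d* = 1, *g* = 0.80 or 1.25: the active-only result is 0.80 or 1.25.
- *d* = 0.80, *g* = 1.25: the active-only result is 0.80 × 1.25 = 1.00, and the effect is hidden.
- *d* = 0.80, *g* = 0.80: the active-only result is 0.64.
- In each case active/placebo returns *d*.

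**Precision.** With *s* = √ln(1 + CV²), where CV is that of the Day 14/Day -1 ratio (assumed), the unadjusted 90% CI is the estimate multiplied and divided by exp[*t*(0.95, n_a + n_p − 2) × *s* × √(1/n_a + 1/n_p)]. For CVs of 15%, 25% and 35%, *s* = 0.149, 0.246 and 0.340.

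| Active : placebo | *t* | √(1/n_a + 1/n_p) | CV 15% | CV 25% | CV 35% |
|---|---|---|---|---|---|
| 6:2 (cohort 2 only) | 1.943 | 0.816 | 1.27 | 1.48 | 1.71 |
| 12:4 (cohorts 2-3) | 1.761 | 0.577 | 1.16 | 1.28 | 1.41 |
| 18:6 (cohorts 2-4) | 1.717 | 0.471 | 1.13 | 1.22 | 1.32 |
| 6:6 (one regimen vs pooled placebo) | 1.812 | 0.577 | 1.17 | 1.29 | 1.43 |

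The comparison costs precision. At an assumed CV of 30%, the factor for the active-only ratio is 1.27 with 6 subjects and 1.13 with 18. For active/placebo it is 1.59 at 6:2 and 1.27 at 18:6.

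**The case against.** A reader might infer that the SAP analyses the ratio only in active subjects. The documents do not support that. No sentence says so, the population wording can be read either way, and by-treatment tables could include placebo. The table layouts are in a separate document that is not available here.

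A reader might also infer that drug effect and confinement are wholly inseparable. That is too strong as well. Foods that alter CYP1A2 are barred from 14 days before check-in, caffeine from 48 h before check-in and nicotine from 90 days before dosing. Medicines acting on CYP1A2 are prohibited, and both probes are given to resident subjects. These controls should shrink a period effect. They do not remove it: compliance before admission is unsupervised, and they do not touch the differences in administration.

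The endpoint is exploratory and descriptive. The stated CYP1A2 objective concerns genotype and phenotype, and the SAP draws no conclusion about TMP-301 from the ratio. Text that might state the purpose of the probe (for example Protocol 1.11.4 and 1.11.5) is redacted. This limits the weight of the point. Even so, this ratio is the plan's only measure of change in CYP1A2 activity.

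Finally, two to six placebo subjects make a thin control, and the 18:6 case needs both optional cohorts. That stands. It is a reason to call the result estimation and to show the within-group ratios beside it, not to omit the comparison.

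**Conclusion.** The point holds as a gap in specification. CYP1A2_ratio is planned only as a descriptive Day 14/Day -1 ratio, the place of placebo subjects is undefined, and no active-versus-placebo estimate is planned. A change seen in active subjects alone cannot be attributed cleanly to TMP-301. The documents do not show that placebo is excluded, nor that a period effect of any particular size exists.

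The size of any bias equals the size of the common shift, which is unknown; 0.80 to 1.25 is only an illustration. The interval factors rest on assumed CVs, equal variance in the two arms and complete data. Cancellation of the shift assumes that it is the same in the groups compared. With 6:2 in every cohort this is reasonable for all active versus all placebo. It is weaker for one regimen against pooled placebo if some cohorts are dosed fed.

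Because the endpoint is exploratory, this should be corrected but does not threaten the trial's primary conclusions.

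**What to change.** In the SAP:
1. Define a caffeine-probe analysis set: all dosed subjects, active and placebo, in cohort 2 onward with both 4-hour samples. State the cohort limit, because the note under Table 2 speaks of enrolled subjects in general.
2. Report the geometric mean Day 14/Day -1 ratio by treatment and for placebo pooled over the caffeine cohorts.
3. Add the active/pooled-placebo ratio of ratios with a 90% CI on the log scale, per regimen and for all active subjects combined. Adjust for the ln Day -1 ratio when numbers allow. If cohorts differ in feeding state, list each cohort's placebo values separately as well.
4. Label this exploratory estimation, with no test or decision rule.

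The cost is SAP wording and one table; the samples are already scheduled. The drawback is a wide interval, above all if cohort 2 is the only caffeine cohort. The change should be made before database lock and unblinding, because SAP section 5 treats any later analysis as post hoc.
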